The findings of the proposed study will have a dramatic impact on clinical practice and will energize the research community to further explore the potential mechanism of action and target organ(s) of this therapy. Demonstration that the rate of PTB is related to plasma 17-OHPC concentration will lead to a different dosing regimen for women with a prior preterm birth. This would impact not only practice in the United States but throughout the world as treatment with 17-OHPC is internationally embraced. Positive findings from this project will have a substantial public health impact. Approximately 133,000 pregnant women annually with a history of a prior preterm birth would be eligible for this treatment.¹⁰ If the preterm birth rate is reduced even 10% from its current rate with the optimized dosing regimen the impact would be substantial. In dollar terms each preterm birth cost nearly \$52,000. Preventing 10% of these 13,000 preterm births will save \$663 million annually. Incremental reductions in preterm birth would lead to comparable changes in financial savings.

Some may suggest that the striking relationship between plasma 17-OHPC concentration and the rate of preterm birth we have reported from the MFMU Omega-3 trial provides sufficient proof to adopt a strategy of merely doubling the standard dose of 17-OHPC. **We strongly disagree** with such a strategy because all women in our study received Omega-3 supplementation and the impact of this supplement on the metabolism and plasma concentration and efficacy of 17-OHPC is not completely clear. Furthermore, as a secondary analysis the Omega-3 study was not designed to address the relationship between plasma concentrations of 17-OHPC and the outcome of preterm birth. The Omega 3 trial utilized only weekly injections of 250 mg of 17-OHPC and therefore data from this trial cannot address the issues of what impact higher plasma concentrations would have on the PTB rate. Recently, another study evaluated the relationship between 17-OHPC concentrations and preterm birth and a concentration relationship with the rate of preterm birth could not be demonstrated²⁸. These findings emphasize the need for a prospective study that relates plasma 17-OHPC concentrations and PTB rates.

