The proposed research will shift both fundamental research and clinical practice paradigms. Paradigm is defined by Webster as “a model for something that may be copied or a group of ideas about how something should be done, or thought about”. The proposed study will clearly challenge two existing paradigms; one related to the regulation of parturition and the second related to the study of medications in pregnancy. The demonstration of a relationship between dose or concentration of 17-OHPC and the outcome of preterm birth will not only impact the clinical care of women at risk for preterm birth but will also impact the scientific community and the long held concepts of what regulates human parturition. Progesterone withdrawal preceding parturition is a characteristic of most mammalian species except humans, monkeys and guinea pigs.²⁶ In humans, progesterone concentrations increase as pregnancy progresses and do not fall prior to labor onset. Plasma progesterone concentrations are high and in excess of concentrations required to half saturate (EC50) the progesterone receptor. The suggestion that progesterone supplementation might delay human parturition, therefore, seems biologically improbable. However, several clinical trials have demonstrated a benefit with progesterone supplementation in certain conditions. A benefit is seen with 17-OHPC in women with prior preterm birth but not in women with twin or triplet gestation or a shortened cervix.^{4,29-31} Vaginal progesterone appears to confer benefit to women with a shortened cervix but not to women with prior preterm birth.^{13,32,33} Each of these clinical trials has been subject to criticism and skepticism abounds. For 17-OHPC, only a single large trial has shown benefit and in that trial the rate of preterm birth in the control group was much higher than expected leading some to suggest that the medication did not provide a benefit as the preterm birth rate in the 17-OHPC group was identical to the rate reported in other studies in women with a prior preterm birth and no treatment.^{4,34} Vaginal progesterone appears to reduce preterm birth in women with a shortened cervix but this treatment failed to gain FDA approval because, in the opinion of the FDA, the study failed to demonstrate benefit in women residing in the United States. Thus, although clinical trials suggest that progesterone supplementation may impact the parturitional process, proof of concept is clouded. If the proposed study demonstrates a concentration relationship between 17-OHPC and preterm birth rates, then the role of progesterone as a regulator of human parturition will be established

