The primary outcome will be the rate of preterm birth (<37 weeks) according to the plasma concentration of 17-OHPC (as a continuous variable) from the 26-30 week sample. The distribution of plasma concentration is expected to be highly positively skewed; thus, a natural logarithmic transformation will be applied to plasma concentrations to produce normally distributed values. A Cox proportional hazard model will be employed to analyze the effect of continuous log-transformed plasma concentration on event-free survival (in this case, “event-free survival” meaning “not birthed until term”). Specifically, the hazard of delivering preterm will be modeled as a function of log-transformed plasma concentration and additional covariates that may influence treatment effectiveness (e.g., BMI, race, gestational age at study entry). Adjusted survival curves will be calculated using the relationship between the hazard function and the survival function. A Wald test will be performed to determine whether the hazard ratio corresponding to a one-unit increase in log-transformed plasma concentration is significantly different from zero. Wald and likelihood ratio tests will also be employed to test for the significance of additional covariates, and stratified analyses may be considered if appropriate (i.e., race-specific analyses). This semi-parametric modeling approach will allow us to analyze the effect of, and not just the presence of, covariates on event-free survival in a robust manner.

Secondary outcomes that are also survival outcomes (such as spontaneous PTB, spontaneous PTB before 32 weeks and before 35 weeks, and indicated PTB) will be analyzed in a similar fashion to the primary outcome analysis described above. For other secondary outcome measures that are continuous variables (maternal and infant hospital days, maternal and fetal plasma concentrations of progesterone, hydroxyprogesterone, 17-OHPC and its metabolite, etc.), linear regression models with appropriate covariates will be utilized.

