Based on the simulated distribution of 17-OHPC plasma concentration at higher doses in this study, we expect the variance of log-transformed concentration to be 0.226. Given the results of the prior study, we have estimated the hazard ratio corresponding to a one-unit increase in log-transformed 17-OHPC concentration to be 0.49. We also anticipate that 28% of study participants will deliver preterm. Thus, a Cox regression based on a sample of 208 women will have 80% power at the $\alpha=0.05$ significance level to detect a hazard ratio of 0.49. This sample size will be adjusted for the presence of other covariates in the Cox model; assuming that additional covariates such as BMI account for 30% of the variation in log-transformed plasma concentration, we require a sample size of **296 women** to achieve 80% power (Table 1). Our

published data indicate that only maternal BMI affects plasma concentrations of 17-OHPC and accounts for no more than 30% of the variation in plasma concentrations (Figure 7). We will recruit 300 subjects overall to account for non-compliance or non-collection of plasma for analysis of 17-OHPC. Data from non-compliant subjects will not be used for any analysis related to plasma 17-OHPC concentration. In addition, data analysis related to plasma 17-OHPC concentration in those subjects who stop 17-OHPC treatment because of a drug allergy, thrombosis or cholestatic jaundice will not be utilized, but their outcomes will be kept and included in the secondary outcomes that are not related to plasma 17-OHPC concentrations. The sample size will be sufficient to address secondary outcomes since the variation in the variables studied will be far smaller than the variation in plasma 17-OHPC concentration.

All three centers have recruited very well in other studies of 17-OHPC from the MFMU. The pool of subjects annually available for recruitment will exceed 300. Even at a study acceptance rate as low as 30%, there are more than enough subjects to enable us to reach our recruitment goal. We anticipate an acceptance rate closer to 50%. All power analyses were performed using PASS 13. [CITE: PASS 13 Power Analysis and Sample Size Software (2014). NCSS, LLC. Kaysville, Utah, USA, ncss.com/software/pass.]

Table 1. Total Sample Size Required for 80% Power

		% variation accounted for by additional covariates			
		0%	10%	20%	30%
% participants delivering preterm	26%	223	248	279	319
	27%	215	239	269	307
	28%	208	231	259	296
	29%	200	223	250	286

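### The primary slope pools randomised (dose) and non-randomised (within-dose) differences in concentration, so a positive result cannot by itself support the dosing and causal statements in section B.6

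*Combined protocol and SAP*

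**What the plan says.** Section B.6 argues against doubling the dose on the strength of the earlier Omega-3 association. One reason given is that only 250 mg was used there, so those data "cannot address the issues of what impact higher plasma concentrations would have on the PTB rate". This trial therefore randomises women 2:1 to 500 mg or 250 mg (section C.2). B.6 then states what a positive result will mean: "Demonstration that the rate of PTB is related to plasma 17-OHPC concentration will lead to a different dosing regimen". It adds that if a concentration relationship is shown, "then the role of progesterone as a regulator of human parturition will be established", and puts this as being past doubt.

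The primary analysis in D.1 is preterm birth "according to the plasma concentration of 17-OHPC (as a continuous variable) from the 26-30 week sample". In the model, "the hazard of delivering preterm will be modeled as a function of log-transformed plasma concentration and additional covariates that may influence treatment effectiveness"; BMI, race and gestational age at entry are given as examples. The decision rests on one test: "A Wald test will be performed to determine whether the hazard ratio corresponding to a one-unit increase in log-transformed plasma concentration" differs from its null value. Dose is not named in this model.

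D.1 also plans a covariate-adjusted Cox comparison of preterm birth between the dose groups, and lists the effect of dose on spontaneous preterm birth among the secondary outcomes. Section D.2 gives no power for either. Nothing ties the B.6 statements to them.

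**The concern.** Concentration will differ between women for two reasons. One is assigned dose, which is randomised. The other is everything that makes concentrations differ at a fixed dose: BMI (section B.4), possibly co-medication that inhibits metabolism, and other maternal factors. This second part is the same kind of evidence as the Omega-3 association, which B.6 itself calls insufficient for changing the dose.

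One pooled slope averages the two parts. It can be significant on the within-dose part alone, and the B.6 text would still read it as grounds for a new regimen and as causal proof. The randomised arm was added to close that gap, but the plan does not say that the dosing conclusion depends on it.

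**Working it through.** **Inputs.** Expected medians 10 and 20 ng/ml (B.5); allocation 2:1 and 300 women (C.2); variance of log concentration 0.226, hazard ratio 0.49 per log unit, 28% events, covariates explaining 30% of concentration variation, and 208 or 296 women for 80% power (D.2 and Table 1). Two-sided 5% is assumed, because sidedness is not stated.

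**1. The plan's own figure.** Events needed = (1.960 + 0.842)² / (variance × (ln 0.49)²).
- Variance 0.226: 68.25 events; 68.25 / 0.28 = 244 women, or 349 with the 30% adjustment. The plan states 208 and 296.
- Variance 0.266: 57.99 events, giving 208 and 296, and Table 1 to within one woman.

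This mismatch is a separate matter. Both variances are carried below.

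**2. Randomised share of the variance.** Between-dose variance = (1/3)(2/3)(ln 2)² = 0.107.
- Total 0.226: randomised share 47%; within-dose variance 0.119 (53%).
- Total 0.266: randomised share 40%; within-dose variance 0.159 (60%).

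Plausibility check from the Omega-3 data in B.5 (median 9.9 ng/ml), assuming log-normality: 5% above 20 ng/ml gives (ln(20/9.9)/1.645)² = 0.18, and a top-quartile median of 15 ng/ml gives (ln(15/9.9)/1.150)² = 0.13. The within-dose variances used here are at or below that range.

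**3. Illustrative worst case.** Suppose dose has no effect and the within-dose hazard ratio of 0.49 is entirely confounding. Then pooled log HR = (within-dose share) × ln 0.49, and the chance of a significantly protective result = Φ(|pooled log HR| × √(84 × V) − 1.96), where V is the variance left after adjustment and 84 = 300 × 0.28.

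| Case | Within-dose variance | V | Pooled HR | Significant |
|---|---|---|---|---|
| Unadjusted, 0.226 | 0.119 | 0.226 | 0.69 | 37% |
| Unadjusted, 0.266 | 0.159 | 0.266 | 0.65 | 52% |
| 30% of total removed, all within-dose, 0.226 | 0.051 | 0.158 | 0.79 | 13% |
| Same, 0.266 | 0.079 | 0.186 | 0.74 | 22% |
| 30% of within-dose removed, 0.226 | 0.083 | 0.190 | 0.73 | 24% |
| Same, 0.266 | 0.111 | 0.218 | 0.70 | 34% |

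The nominal protective rate is 2.5%. Simulated Cox fits (2,000 trials each) gave 38% and 49% for the unadjusted rows. Adding 100 ancillary women, an assumed number, raised these to 46% and 61%. In the simulated unadjusted trials with a positive pooled slope, the dose comparison was also positive in only about 4–6%.

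**4. What the randomised comparison can deliver.** If the 0.49 slope is fully causal, the 500 versus 250 mg hazard ratio is 0.49^(ln 2) = 0.61. The standard error of the log HR is 1/√(84 × 2/9) = 0.23. Power is Φ(0.494/0.231 − 1.96) = 57%. Eighty per cent power needs 145 events, or 518 women at 28%.

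**5. Would a consistency rule work?** Suppose a dosing claim required the dose component to point the same way and the test of equal slopes to be non-significant. In the step 3 scenario, by normal approximation, the equality test rejects in only 34–38% of trials unadjusted. The rule still passes 60–66% of false-positive primary results, and 67–77% after adjustment, because a significant pooled slope selects trials in which the dose estimate is favourable by chance.

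**The case against.** The strongest reply is that the primary objective is associational (section C.2), D.1 sets no rule leading from the Wald test to a regimen, and B.6 is rationale rather than analysis. That is fair as to location. But B.6 is the only place that says what a positive result will be taken to mean, and D.1 does not narrow it.

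A reader might infer that a positive primary result cannot support a dosing conclusion at all, or that the randomised information goes unused. The documents do not support either reading. Randomised dose supplies 40–47% of the variance behind the slope, and D.1 plans an adjusted dose comparison that readers will see.

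The worst case is also extreme. No figure in the documents shows that the earlier association was wholly confounded, and B.5 reports that the quartile association persisted after adjustment for BMI, race and ethnicity, and gestational age at entry and at sampling. Persistence after adjustment for measured factors does not show causality either.

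The planned model is adjusted, so the adjusted rows matter more than the unadjusted ones. A reader might shrink both variance components by 30%, which gives 28–39%. That is not right: baseline covariates are independent of randomised dose in expectation and cannot absorb its variance.

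Trough sampling after at least seven injections, weekly contact, vial counts and exclusion of non-compliant women narrow the sources of confounding without removing them. Adding dose as a covariate, which D.1 does not rule out, would leave a purely within-dose slope, which is weaker support for a regimen statement.

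**Conclusion.** The point holds in this form: a significant pooled slope cannot by itself support the B.6 statements on dosing or on a causal role. Between 53% and 60% of the expected variance in log concentration is not randomised. With no dose effect at all, the primary test could be significantly protective in about 13–34% of trials after adjustment (37–52% unadjusted).

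Those percentages illustrate a worst case and do not predict what will happen. They assume log-normal concentrations, equal within-dose variance in both arms, 28% events, no exclusions and a within-dose association due wholly to confounding. The variance split does not depend on that last assumption. The conclusion holds at either variance, 0.226 or 0.266. It does not mean that the primary test is invalid as a test of association, or that the earlier association was spurious.

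**What to change.** Keep the primary test as it is, and add the following to D.1.

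- In randomised women only, with the ancillary cohort excluded, pre-specify a companion Cox model that splits log concentration into the mean for the assigned dose and each woman's deviation from it. Report both hazard ratios per log unit with confidence intervals, and the test of equality descriptively.
- Beside it, show the planned dose contrast in all randomised women, including the non-compliant women whom C.7.ii and D.2 remove from concentration analyses.
- State that a significant pooled slope is reported as an association, and that any dosing statement rests on the randomised dose estimate and its confidence interval. Bring the B.6 wording into line.
- Do not use agreement in direction plus compatibility as a gate, given step 5 of the working.

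The cost is one extra model and a few sentences, with no new data. The downside is precision: with a standard error of about 0.23 on the log hazard ratio and about 57% power, the trial may have to make a more modest claim about dose.

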10. Known or suspected breast cancer, other hormone-sensitive cancer, or a history of these conditions.
11. Moderately severe depression (PHQ-9 score ≥ 15 , EPDS score of >13 , or suicidal ideation)- based on criteria in the RCT

C.3.ii. Gestational Age Determination

We will use the criteria recommended by the American Congress of Obstetricians and Gynecologists (ACOG)³⁷.

C.4. Informed Consent Procedures and Documentation

Written informed consent will be obtained before entry into the trial. Full disclosure of the nature and potential risks of participating in the trial will be made. Each center will develop its own consent form according to the requirements of its IRB. Women who are not fluent in English will be enrolled by a person fluent in their language and both verbal and written

informed consent obtained in that language; if such are not available, they will not be included.

C.5. Randomization Procedures

Eligible and consenting women will be enrolled and randomized by clinical site and prior preterm birth history (based on earliest SPTB, dichotomized to 30 weeks or less or >30 weeks) to the standard 17-OHPC dose of 250 mg or to a dose of 500 mg intramuscularly weekly starting at 16 0/7 – 21 6/7 weeks and continuing till 36 6/7 weeks gestation. We will stratify at randomization by site and pregnancy history due to the dramatic ethnic, racial and socioeconomic differences in the population at the 3 centers and the demonstrated impact of gestational age at a prior preterm birth on subsequent pregnancy duration. This will be an open label study. Blinding is not required since the primary outcome of interest is the rate of preterm birth according to plasma concentration achieved. Knowledge of the dose by the provider or subject does not impact the primary outcome, i.e., the rate of preterm birth or the plasma concentration. We will not stratify subjects at randomization by any maternal variables since an objective of the study is to define which maternal characteristics might impact 17-OHPC concentrations or efficacy. Our prior work demonstrates a clear impact of maternal BMI but this effect is modest i.e., ~17%.³⁸

Subjects enrolled in the ancillary cohort will not be randomized as they are already on the 250 mg dose.

C.6. Study Procedures

C.6.i. Study Drug Dispensation

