At randomization, we will record height and weight from the medical record and collect information about demographics (e.g., age and race), social history (e.g., marital status, years of education, alcohol use, tobacco use and illicit drug use), medical and obstetric history, prenatal labs and ultrasound findings from the index pregnancy, and concomitant medication and supplement use. Self-reported information will be confirmed with the medical record. This visit is anticipated to last approximately 30 minutes.

C.6.iii. Study Visits

- **Randomized Clinical Trial:**

Each center will see subjects enrolled in the RCT every 6-9 weeks to provide additional medication and to perform other aspects of the study including examination of the injection sites, as needed. All subjects in the RCT will have venous blood draws performed at the times described in the protocol. Research staff will contact subjects weekly to record injection information, ask about possible side effects of the medication experienced since the last injection, and about the use of other medications. They will also ask about any hospitalizations and any pregnancy complications that have been diagnosed since the last contact. If complications of the pregnancy arise, such as need for a cervical cerclage, or need for vaginal progesterone, they will be recorded. If the patient is hospitalized for any reason including preterm labor, treatment should continue. The local principal investigator will evaluate the event's expectedness, relatedness and severity. Events will be reported to the local IRBs per institutional procedures and the participating investigators and FDA, as required. Details of monitoring, documenting and reporting serious adverse events (SAEs) will be documented in the study's safety monitoring plan. Weekly communication will occur until the patient delivers.

Subjects in the RCT will be assessed for depression using either the Patient Health Questionnaires (PHQ-2 and PHQ-9, if required) or the Edinburgh Postnatal Depression Scale (EPDS)⁴⁰ at the following study visits when maternal blood samples are collected: Screening Visit, 26-30 week visit, and 6-9 weeks after the 26-30 week visit.

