Research staff will contact subjects weekly to record injection information, ask about possible side effects of the medication experienced since the last injection, and about the use of other medications. They will also ask about any hospitalizations and any pregnancy complications that have been diagnosed since the last contact. If complications of the pregnancy arise, such as need for a cervical cerclage, or need for vaginal progesterone, they will be recorded.

C.6.iv. Delivery

At delivery, pregnancy and neonatal outcome information will be obtained from the medical record. Biological samples will not be collected at delivery for subjects in the ancillary cohort.

C.6.v. Specimen Collection

a. RCT Specimen Collection

Maternal blood will be collected on four occasions by a health care provider or research staff trained in phlebotomy:

1. Prior to the 2nd injection (1 tube of 7 ml), ideally on day 7 from the first injection
2. Between 26-30 weeks - but only after a minimum of 7 injections have been administered (1 tube of 7 ml will be drawn just prior to the next injection; this will be a trough level)
3. Between 6-9 weeks after the 26-30 week specimen but not later than 37 weeks (1 tube of 7 ml will be drawn just prior to the next injection; this will be a trough level)
4. At delivery (1 tube of 7 ml), when possible

A second tube of blood (7 mL) will be drawn with any of the first 3 blood draws for genotyping of various genes related to preterm birth if mother consents to this optional test.

Umbilical cord blood (7 mL) will be collected at delivery. A second cord blood specimen (7 ml) will be drawn for genetics studies in the baby if mother consents. These blood specimens will be collected, when possible, and used to determine the concentrations of various biochemicals, 17-OHPC and its metabolites, and for genetic studies.

A 3 x 3 cm piece of placenta will be collected, when possible, for p-glycoprotein and other transporters.

Labor and Delivery biological specimens will be collected when possible. All biological specimens will be frozen at -70 to -80° C and stored locally until assayed at the University of Pittsburgh.

b. Ancillary Cohort Specimen Collection

Maternal blood will be collected on two occasions by a health care provider or research staff trained in phlebotomy:

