C.9. Medical monitor and Logistic Coordinating Core

A Medical Monitor has been selected for this trial. The Medical Monitor will receive reports from each clinical center which will be compiled by the NICHD funded **Logistic Coordinating Core (LCC)**. The LCC facilitates and coordinates the OPRC clinical study activities and ensures that all activities are implemented.

The role of the Medical Monitor will include:

- Ongoing monitoring of SAE reports submitted by the clinical centers to identify safety concerns and suggest protocol modifications, if necessary
- Advise IND sponsor, Principal Investigator(s), and DMC regarding SAEs and safety concerns
- Provide reports when necessary to the Principal Investigator and DMC

D. Statistical Analysis and Sample Size Justification

D.1. Primary and Secondary Outcomes

The primary outcome is the rate of preterm birth (delivery prior to 37 0/7 weeks) according to 17-OHPC concentration.

Secondary outcomes include:

- The rate of spontaneous PTB prior to 32 0/7 and 35 0/7 weeks according to the concentration of 17-OHPC.
- The impact of dose, race, BMI and co-medications on plasma 17-OHPC concentrations
- Plasma concentrations of 17-OHPC, mono-hydroxylated metabolite of 17-OHPC
- Concentrations of progesterone and 17-hydroxyprogesterone in maternal and cord blood according to the weekly dose of 17-OHPC
- The frequency of maternal side effects according to dose and plasma concentration
- The frequency of neonatal complications according to dose and plasma concentration
- Impact of dose on rates of spontaneous PTB
- The correlation of progesterone and 17-hydroxyprogesterone in maternal plasma and whole blood to pharmacological and clinical outcomes

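### The weekly side-effect question looks back only to the last injection, so how much of each week it covers depends on a contact day that the protocol does not fix

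*Combined protocol and SAP*

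**What the plan says.** In C.6.iii (Study Visits, Randomized Clinical Trial) the weekly contact has two recall windows. For side effects: "Research staff will contact subjects weekly to record injection information, ask about possible side effects of the medication experienced since the last injection". For other events the window is different: staff ask about "any hospitalizations and any pregnancy complications that have been diagnosed since the last contact". The ancillary-cohort text in the same section repeats both sentences.

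The contacts outlast the injections. C.5 has weekly injections "continuing till 36 6/7 weeks gestation", while C.6.iii states that "Weekly communication will occur until the patient delivers".

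C.6.i lets research staff, office staff or a trained lay person at home give the injection, with 6-9 weeks of drug supplied for home use. It presents the weekly contact as the means by which every injection gets recorded. No section says on which day of the injection cycle the contact falls.

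The answers feed secondary research question 2 (C.2) and a secondary outcome in D.1: "The frequency of maternal side effects according to dose and plasma concentration".

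**The concern.** Two consecutive sentences about the same contact use different reference points, and only one of them leaves no gap between contacts. A window that starts at the last contact joins up with the previous window whatever the day. A window that starts at the last injection joins up only if staff ask just before the next injection. When the contact comes earlier in the cycle, the days between it and the next injection are not asked about then. They are not picked up later either, because the next contact looks back only to the newer injection.

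Home injection makes this a realistic case, since staff then learn through the contact of an injection already given. Pharmacology does not justify the shorter window: B.4 gives a half-life of 16.2 days, so one week is 7/16.2 = 0.43 of a half-life and exposure continues through the unasked days.

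At stake is the completeness of routine side-effect data for a 500 mg dose that C.8 describes as not FDA approved. The weekly question is the only routine side-effect enquiry that the protocol describes. In-person visits are 6-9 weeks apart, and injection sites are examined only as needed. The protocol gives no rule for dating an effect, merging repeat reports, or choosing between women affected and reports made.

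**Working it through.** The plan states no figure on this point, so there is none to reproduce. The check is interval arithmetic.

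**Inputs.** Injections every 7 days, ending by 36 6/7 weeks (C.5). Contacts weekly until delivery (C.6.iii). The lag d from injection to contact is not in the documents, so it is taken over its whole range, 0 to 7 days.

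**1. During treatment.** Days asked about = d; days not asked about = 7 - d; share covered = d/7.

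| Lag d (days) | Asked | Not asked | Share covered |
|---|---|---|---|
| 0 | 0 | 7 | 0% |
| 1 | 1 | 6 | 14% |
| 2 | 2 | 5 | 29% |
| 3 | 3 | 4 | 43% |
| 4 | 4 | 3 | 57% |
| 5 | 5 | 2 | 71% |
| 6 | 6 | 1 | 86% |
| 7 (just before the next injection) | 7 | 0 | 100% |

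**2. A missed contact.** The next contact comes 14 days after the last one made but still looks back only d days, so 14 - d days go unasked. Even at the best lag, d = 7, that is 7 of 14 days.

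**3. After the final injection.** Let L be the day of the last injection and g the day of delivery, both in days of gestation. The contacts that look back to L are those at L + d + 7k < g, for k = 0, 1, 2, and so on. Example: L = 252 (36 0/7), d = 3 and g = 273 (39 0/7) give contacts on days 255, 262 and 269, which is three. Ranges over lags of 1 to 7 days:

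| Delivery at | Last injection 36 0/7 | Last injection 36 6/7 |
|---|---|---|
| 37 0/7 | 0-1 | 0 |
| 38 0/7 | 1-2 | 1 |
| 39 0/7 | 2-3 | 2 |
| 40 0/7 | 3-4 | 3 |
| 41 0/7 | 4-5 | 4 |

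The number of contacts opening the same window therefore runs from 0 to 5. The first is not a repeat, so an early effect could be reported again at most 5 - 1 = 4 times. A woman who delivers before 37 weeks with injections into week 36 has at most one such contact, hence no repeat.

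**4. With a window since the last contact.** Each interval between contacts is asked about exactly once at any lag. A missed contact only lengthens the next window (14 of 14 days covered), and nothing repeats after the final injection. The days between the last contact and delivery go unasked under either wording.

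**The case against.** The strongest reply is that the contact day is simply unstated. Where staff give the injection, asking just before it is a natural reading and loses nothing. A contact just before the next injection also serves to record the previous one. This stands: a reader might infer that part of most weeks goes unasked, but coverage can be anywhere from 0% to 100% and the documents do not say where it lies.

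A reader might also infer that the dose comparison is biased, because home and staff injection could lead to different contact timing. The documents do not support that. Dose is randomized, C.6.i offers both arms the same choice of injector, and nothing shows that timing differs by arm. If coverage is equal and effects fall at similar points in the cycle, the ratio of event rates is not distorted. What is lost is events.

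A third tempting inference is that repeat questions after the last injection would imitate a concentration effect, since term delivery is expected to be commoner at higher concentrations. That needs an analysis of unmerged reports. D.1 does not say that reports will be counted, and re-asking cannot raise the share of women ever affected.

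Other limits also stand. An effect that persists past the next injection would still be picked up at the following contact. Hospitalizations and complications are asked about since the last contact, serious adverse events have 24-hour reporting (C.8), and the DMC reviews adverse events every 4 months. The case report forms (E.2) are not in the documents and may already carry onset dates or a different question.

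This does not answer the core point: the written rule leaves a gap at every lag short of 7 days, and after any missed contact.

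**Conclusion.** The concern holds as a minor, readily corrected flaw in data collection. Followed literally, the side-effect window covers d/7 of each week and can miss transient, non-serious effects that begin and end between a contact and the next injection. Such losses can lower the share of women ever affected as well as the number of events. After the final injection, 0 to 5 contacts share one window, so a count of unmerged reports can be inflated in women who deliver at term.

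The coverage figures rest on a literal reading and on a lag that the documents do not give. The range of 0 to 5 assumes injections into week 36 and delivery by 41 0/7. A woman who stops treatment earlier but stays in the study (C.7.i) could have more such contacts.

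It would go too far to say that the side-effect frequencies will be wrong. Their actual error depends on contact timing and a counting rule that the documents do not state. Serious events are largely protected, and the primary outcome does not use these data.

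**What to change.** In the RCT text of C.6.iii, make the side-effect question run from the last contact, as the following sentence already does for hospitalizations and complications. Make the same edit in the ancillary text for consistency only, since C.2 excludes those data from research question 2.

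On the weekly contact form, record the onset date of each side effect and the date of the last injection. Timing relative to the injection can then be derived in the analysis. In D.1, state that each effect is counted once by onset date, and whether the reported frequency is of women affected or of events.

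The cost is one phrase in the protocol, the matching change to the form, and two date fields if the form lacks them. No extra visits, staff or participants are needed. Records already collected under the current window cannot be reliably completed afterwards and should be flagged in the analysis.
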